- m. Remote contact (text message by sms, WhatsApp or email) on Day 3 and on Days 21, 31 and 49 for safety follow-up and reminder stool collection scheme.
- n. Adverse events and intake of concomitant medication(s) will be monitored continuously from informed consent until the last study-related activity. The subjects can record unsolicited AEs on their diary card.
- o. After signing on screening visit, weekly reminder Code of Conduct by email or sms and on each visit to emphasize the need and importance of hygienic measures and respecting the inclusion/exclusion criteria until end of study.

LIST OF ABBREVIATIONS AND DEFINITIONS OF TERMS

List of Abbreviations

AE	Adverse event
ALT	Alanine Aminotransferase
AMA	Anti-Mitochondrial antibodies
ANA	Anti-Nuclear antibodies
AST	Aspartate Aminotransferase
bpm	Beats per minute
CCID ₅₀	50% cell culture infective dose
CI	Confidence interval
CK	Creatine phosphokinase (including isozymes)
CRF	Case Report Form
CTCAE	Common Terminology Criteria for Adverse Events
cVDPVs	Circulating vaccine-derived polioviruses
cVDPV2	Circulating vaccine-derived poliovirus type 2
DBP	Diastolic blood pressure
DNA	Deoxyribonucleic acid
DSMB	Data Safety Monitoring Board
eCRF	Electronic Case Report Form
EDC	Electronic Data Capture
GCP	Good Clinical Practice
GGT	Gamma-Glutamyl Transferase
GMT	Geometric mean titer
GPEI	Global Polio Eradication Initiative
HBsAg	Hepatitis B surface antigen
HCV	Hepatitis C virus
HDPE	High Density Polyethylene
HIV	Human immunodeficiency virus
HR	Heart rate
ICF	Informed Consent Form
ICH	International Conference on Harmonization
IEC	Independent Ethics Committee
IME	Important medical event
IMP	Investigational medicinal product
IPV	Inactivated polio vaccine
IRB	Institutional Review Board
LDH	Lactate dehydrogenase
LKM-1	Liver-kidney microsomal type 1 (antibodies)
LSLV	Last Subject Last Visit
MedDRA	Medical Dictionary for Regulatory Activities
mOPV2	Monovalent oral polio vaccine type 2
nOPV2	Novel oral polio vaccine type 2
OPV	Oral polio vaccine
PD50	50% paralytic dose
PP	Per-protocol

RNA	Ribonucleic acid
SAE	Serious adverse event
SAGE	Strategic Advisory Group of Experts on immunization
SAP	Statistical Analysis Plan
SBP	Systolic blood pressure
SD	Standard deviation
SLA/LP	Soluble liver antigen/liver-pancreas (antibodies)
SmPC	Summary of Product Characteristics
SUSAR	Suspected Unexpected Serious Adverse Reaction
tOPV	Trivalent oral polio vaccine
TgPVR	Transgenic mice expressing the cell receptor for poliovirus

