- To assess the safety (serious adverse events [SAEs] and severe adverse events [AEs]) of nOPV2 candidate 1 and nOPV2 candidate 2 in healthy IPV-only vaccinated adults, compared with placebo.

Secondary objectives are

- To assess the safety (any solicited and unsolicited AEs, laboratory assessments) of nOPV2 candidate 1 and nOPV2 candidate 2 in healthy OPV-vaccinated adults, compared with historical controls given Sabin OPV2;
- To assess the safety (any solicited and unsolicited AEs, laboratory assessments) of nOPV2 candidate 1 and nOPV2 candidate 2 in healthy IPV-only vaccinated adults, compared with placebo;
- To compare the immunogenicity (seroconversion rate, median antibody titer (post-vaccination)) of nOPV2 candidate 1 and nOPV2 candidate 2 in healthy OPV-vaccinated adults, with historical control of Sabin OPV2;

* List of severe AEs as mentioned in the diary cards: fever > 39°C, headache, fatigue, myalgia, arthralgia, paresthesia, anesthesia, paralysis, or gastrointestinal symptoms (nausea, vomiting diarrhea and/or abdominal pain) that prevent normal activity or any other severe AE that prevents normal activity.

- To assess the immunogenicity (seroprotection rate, seroconversion rate, median post-vaccination antibody titer) of nOPV2 candidate 1 and nOPV2 candidate 2 in healthy IPV-only vaccinated adults.

Exploratory objectives are

- to compare immunogenicity (geometric mean titer [GMT]) of nOPV2 candidate 1 and nOPV2 candidate 2 in healthy OPV-vaccinated adults, with historical control of Sabin OPV2;
- to assess immunogenicity (geometric mean titer [GMT]) of nOPV2 candidate 1 and nOPV2 candidate 2 in healthy IPV-only vaccinated adults;
- to compare viral shedding following nOPV2 candidate 1 or nOPV2 candidate 2 administration in a pre-specified subset of stool samples in healthy OPV-vaccinated adults, with historical control of Sabin OPV2;
- to assess viral shedding following nOPV2 candidate 1 or nOPV2 candidate 2 administration in a pre-specified subset of stool samples in healthy IPV-only vaccinated adults;

The shedding analyses will initially be conducted using a subset of samples in the 10 days following administration of each dose (e.g. day 0, 3, 5, 7, and 10) and all samples at day 14 and thereafter. The remaining samples will be stored pending evaluation of the initial analyses; PCR and CCID₅₀ will be conducted on these stored samples if deemed important for the complete interpretation of the study results.

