Also, if type 2 virus shedding is detected by PCR on one of the last 3 scheduled stool samples, the study duration for this individual will be extended. As soon as these results are known (anticipated approximately 3 weeks after the last such sample provided for evaluation) the subject will be asked to collect further 3 consecutive stool samples (with a maximum of one sample per day) after the last per-protocol sample, and to repeat this until shedding is PCR-negative for type 2 poliovirus on 3 consecutive stool samples, which then determines study end for this person.

If the last stool sample is missing the subject will be asked to provide a new sample as soon as possible in order to determine their end of study or the need for further stool sample collection according to the collection cadence until shedding is PCR negative on 3 consecutive stool samples.

[†] Updated list will be made available at the start of the study. Study will take in consideration the most recent WHO guidelines.

Criteria for Evaluation:

Assessment of the following endpoints for the 2 candidate vaccines in OPV primed subjects (Groups 1 to 4) will be based on comparison with data obtained in the previously conducted Phase 4 study of Sabin mOPV2 in order to assess immunogenicity and establish an acceptable safety profile in these populations. For the safety endpoint of the IPV-primed subjects (Groups 5, 6) comparison will be made with the data of the placebo group (Group 7).

Primary

Safety: The following endpoints will be evaluated **by group and overall:**

- incidence, type and causality of SAEs and severe AEs throughout the study period.

Immunogenicity:

- seroprotection rate of type 2 polio antibodies at Day 28, following a single dose of nOPV2 candidate 1 (combined Groups 1 and 2).
- seroprotection rate of type 2 polio antibodies at Day 28, following a single dose of nOPV2 candidate 2 (combined Groups 3 and 4).
- Seroprotection is defined as type 2-specific antibody titers $\geq 1:8$.

Secondary

Safety: The following endpoints will be evaluated **by group and overall:**

- incidence, type, causality and severity of solicited adverse events for days 0-7 in Groups 1 and 2 combined and days 28-35 in Group 2;
- incidence, type, causality and severity of solicited adverse events for days 0-7 in Groups 3 and 4 combined and days 28-35 in Group 4;
- incidence, type, causality and severity of solicited adverse events for days 0-7 and days 28-35 in Groups 5, 6 and 7;

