For each subject, viral shedding PCR positivity will be determined at a pre-specified subset of the stool collection time points, and the rate of positivity (percent positive of those samples provided which are positive for type 2) will be computed. Additionally, the CCID₅₀ of shed virus will be obtained for each PCR-positive sample and summarized. Also, a viral shedding index will be calculated as the average of log₁₀-transformed values of viral titer in stool samples as determined using quantitative PCR (viral identity) and CCID₅₀ (titer) from select stool samples taken following each vaccine dose. Each of these measures will be summarized by group, and combined for Groups 1 and 2 following the first dose, and for Groups 3 and 4 following the first dose.

Safety

Safety parameters and abnormalities will be tabulated and analyzed descriptively.

Adverse Events

Analyses described below will be performed for solicited and unsolicited AEs as well as for SAEs and severe AEs. The original terms used in the designated sections of the eCRFs by Investigators to identify AEs will be fully described and coded according to the current Medical Dictionary for Regulatory Activities (MedDRA). For comparison with the M1 study M1 data will be recoded if necessary.

All AEs will be summarized by group (combined within vaccine group, where relevant), occurrence in relation to vaccination, and overall.

Separate tables and listings will be created for those subjects who died, discontinued the study vaccine due to an AE, or experienced a severe or serious AE. Summaries, listings, and narratives may be provided, as appropriate.

Clinical Laboratory Tests

Each continuous biochemistry and hematology laboratory test will be evaluated by means of descriptive statistics (i.e., number of subjects, mean, SD, median, minimum, and maximum) on the actual values, at each assessment time point and by group. Changes from baseline will also be summarized by assessment time point and by group, and combined groups, wherever relevant.

Clinical laboratory test values will be evaluated according to Common Terminology Criteria for Adverse Events (CTCAE) version 4.03 (toxicity grades) or in accordance with the normal ranges of the clinical laboratory (below, within, or above normal range) for parameters for which no toxicity grades are defined.

A listing of subjects with any clinical laboratory test result outside the reference ranges will be provided.

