Solicited systemic AEs (Diary) ^k	X-----X				
Remote contact for safety follow-up ^m					
Concomitant therapies ⁿ	X	X	X	X	X
Adverse events ⁿ	X	X	X	X	X
Reminder Code of Conduct ^o	X	X	X	X	X

a. In case of early termination the subjects will be asked to return to the clinical site within 14 days after discontinuation for assessments as outlined on Day 28.

b. No study-related assessment is to be carried out before signing of the informed consent form.

c. Including polio vaccination history.

d. Includes weight and height at Day 0. After Day 0, symptom-directed physical examination.

e. Prior to vaccination.

f. Blood pressure and heart rate (supine) and oral body temperature. On Day 0, vital signs will be assessed prior to and 30 min after vaccination.

g. For a list of assessments, please see Appendix 1: Overview of Laboratory assessments.

h. In women of childbearing potential, a urine pregnancy test will be performed.

i. Includes HBsAg, anti-HCV and anti-HIV antibodies and IgA.

- j. The subjects will be kept under medical supervision for at least 30 min after vaccination.
- k. Solicited AEs will be collected for Days 0-7.
- l. Subjects will be asked to collect the first stool of every day in the provided container and to store this in the provided thermal bag with cooling elements: daily collection on Days 0 to 10 plus collection on Days 14, 21, V4 minus 1 or 2 days and V5 minus 1 or 2 days. At Day 0, the storage procedure will be explained and the collection material provided. Subjects who are still shedding virus in one of the 3 last stool samples will be asked to collect 3 consecutive stool samples every 3 weeks till end of shedding.
- m. Remote contact (text message by sms, WhatsApp or email) on day 3 and on Day 21 for safety follow up and reminder stool collection scheme .
- n. Adverse events and intake of concomitant medication(s) will be monitored continuously from informed consent until the last study-related activity. The subjects can record unsolicited AEs on their diary card.
- o. After signing on screening visit, weekly reminder Code of Conduct by email or sms and on each visit to emphasize the need and importance of hygienic measures and respecting the inclusion/exclusion criteria until end of study.

TIME AND EVENTS SCHEDULE – GROUPS 2, 4, 5, 6 AND 7

Assessments	1	2	3	4	5	6	7	8
Visit	1	2	3	4	5	6	7	8
Time of Visit (days)	D0	D7 (+/- 2D)	D14 (+/- 3D)	D28 (+/- 2D)	D35 (+/- 2D)	D42 (+/- 3D)	D56 ^a (+/- 2D)	D 70 (+/- 4D)
Visit window								

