6.7.1 Exploratory Viral Shedding Endpoints

Throughout, viral shedding analyses will be conducted by group and dose number. The descriptive summaries below will also be computed separately by site. Between-group inferential analyses will additionally be conducted among the site in common between UAM1 and UAM4, for OPV-vaccinated subjects, if the post-dose-1 between-site GMT comparison indicates a significant difference in immunogenicity between sites. The shedding analyses will be conducted considering all available samples, collected at Days 0-10, 14, 21, 28, and 42 following each dose (with day of vaccination defined as Day 0) and additional samples collected, as necessary, to define the end of shedding for participants. All viral shedding data will be listed, including both sample collection and assay results.

Categorical summaries of type 2 viral shedding positivity (positive via PCR) and continuous summaries of viral titers (\log_{10} CCID₅₀/g among both shedders and shedders/non-shedders combined) will be produced by group and by post-vaccination day. Each of these will be augmented with two-sided 95% confidence intervals. The Clopper-Pearson exact method will be used for shedding positivity rate, and the bootstrap method (10,000 replicates, quantile method) will be used for the median \log_{10} viral titers. Subjects who are PCR-negative for viral shedding at a given time point will be assigned the value of 0 for computations involving the \log_{10} CCID₅₀/g, and values PCR positive for type 2 poliovirus but below LLOQ ($2.75 \log_{10}$ CCID₅₀/g) or above ULOQ ($8.25 \log_{10}$ CCID₅₀/g) will be assigned the corresponding value of LLOQ or ULOQ.

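### By-day shedding positivity and combined titre after about Day 42 will be overstated, because almost only subjects with a recent PCR-positive stool are still being sampled

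*Protocol*

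**What the plan says.** **Scheduled stools.** In the one-dose groups every subject is asked for "daily collection on Days 0 to 10 plus collection on Days 14, 21, V4 minus 1 or 2 days and V5 minus 1 or 2" (the closing figures count days before the visit; Time and Events Schedule, Groups 1 and 3). The two-dose groups follow the same pattern after the second dose. The last three scheduled stools therefore fall at about Days 21, 26-27 and 40-41 after the last dose; SAP 6.7.1 labels the last two Day 28 and Day 42.

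**Later stools.** A subject is kept on "if type 2 virus shedding is detected by PCR on one of the last 3 scheduled stool samples" (synopsis, Study/Treatment Duration; same rule in protocol section 9.1). Further stools are requested once the results are known, "anticipated approximately 3 weeks after the last such sample provided for evaluation", and this repeats until three consecutive stools are PCR-negative. The only other source of late stools is a subject whose last sample is missing.

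**Analysis.** The synopsis computes positivity over samples provided: "the rate of positivity (percent positive of those samples provided which are positive for type 2) will be computed". It says that "viral shedding PCR positivity will be determined at a pre-specified subset of the stool collection time points", and its account of the samples to be tested keeps "all samples at day 14 and thereafter". SAP 6.7.1 takes all available samples, names the scheduled days, and adds "additional samples collected, as necessary, to define the end of shedding for participants". Positivity and titre summaries "will be produced by group and by post-vaccination day", with titre shown both among shedders and for shedders and non-shedders together. A titre of 0 goes only to a subject found PCR-negative at the time point. SAP 5.3 assumes data are missing completely at random and does not impute.

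**The concern.** Up to the last scheduled stool, sampling does not depend on the result. After it, sampling depends directly on earlier PCR positivity. A subject whose last three scheduled stools were negative gives no further sample and so appears in neither the numerator nor the denominator of any later day. The by-day rate then describes the retained subjects, while the table is labelled by vaccine group. The missing-completely-at-random assumption cannot hold for these days, because the protocol's own rule decides who is missing.

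At stake is how a reader of the study report interprets late shedding. Protocol Appendix 4 defines long-term shedders by a positive stool after Day 42, so these days will attract attention. The overstatement is greatest where the fewest subjects are retained. Comparing late by-day rates between candidates, or between OPV- and IPV-primed groups, would therefore mislead as well.

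**Working it through.** The documents give no target or expected shedding rate, so there is no planned figure to reproduce. The check has two parts.

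**1. Denominator identity (no duration model).** Let f be the fraction of a group still sampled on a late day and y the share of those who are PCR-positive. Assume that subjects already released are negative.

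- Positivity over samples provided = y
- Positivity over all subjects = f × y
- Ratio = y / (f × y) = 1/f

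The ratio depends on neither group size nor y. It is 5 at f = 20%, 10 at f = 10% and 20 at f = 5%; these values of f are assumed for illustration.

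**2. Illustration with shedding durations.** Inputs:

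- Median durations of about 2 and 4 weeks, from the Phase 1 study in IPV-only adults (protocol 1.3.1).
- Exponential durations (assumption): S(d) = 0.5^(d/median).
- Extension if still shedding at Day 21, the earliest of the last three scheduled stools.
- First follow-up stools at about Day 42 + 21 = Day 63. A second round at about Day 84 (assumption), given only by those positive at Day 63.

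| | Median 14 days | Median 28 days |
|---|---|---|
| f, first round = S(21) | 35.4% | 59.5% |
| Last scheduled stool, S(42) | 12.5% | 35.4% |
| Day 63, all subjects, S(63) | 4.4% | 21.0% |
| Day 63, samples provided, S(63)/S(21) | 12.5% | 35.4% |
| Factor, 1/S(21) | 2.8 | 1.7 |
| Day 84, all subjects, S(84) | 1.6% | 12.5% |
| Day 84, samples provided, S(84)/S(63) | 35.4% | 59.5% |
| Factor, 1/S(63) | 22.6 | 4.8 |

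For a group of 44 with median 14 days, 44 × 0.3536 = 15.56 subjects are extended and 44 × 0.0442 = 1.94 are truly positive at Day 63. The table would show 1.94/15.56 = 12.5%, against 1.94/44 = 4.4%. With a shorter assumed median of 7 days, f = 12.5% and the first-round factor is 8.0 (1.6% against 0.2%).

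Under this model the first-round figure equals the rate at the last scheduled stool, because S(63)/S(21) = S(42). The series appears to level off when it is in fact still falling.

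**Titres.** A simulation of 200,000 subjects used the same durations and an assumed titre in shedders of mean 4, SD 1 on the log10 scale, limited to 2.75-8.25. The Day 63 combined mean titre was 0.49 over samples provided against 0.17 over all subjects (median 14 days), and 1.43 against 0.85 (median 28 days): the same factors, 2.8 and 1.7. The mean titre among PCR-positive samples was 4.05 under both denominators.

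**The case against.** The strongest reply is that the SAP does not clearly promise a table for days after 42. It names Days 0-10, 14, 21, 28 and 42 and gives the extra stools a purpose, defining the end of shedding, which is the Kaplan-Meier endpoint. Follow-up stools fall on scattered days. The synopsis sentence on positivity is written per subject and refers to a pre-specified subset of time points. This correctly places the problem in SAP 6.7.1, with the synopsis supplying only the denominator. It does not remove the problem: SAP 6.7.1 puts the extra stools into the shedding analyses and tabulates by day without a last day, and SAP section 2 says every specified analysis will be performed.

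Several stronger readings are tempting, and the documents do not support them:

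- *Positivity jumps up after Day 42 in every group.* The illustration gives a plateau at the first round; a rise comes only in later rounds.
- *All late titres are inflated.* Titres among PCR-positive samples are not. The combined median stays 0 until reported positivity passes 50%, which in the illustration happens only at the second round with median 28 days (59.5%).
- *These rates drive travel restrictions or household monitoring.* Protocol 1.3.1 and Appendix 4 tie both to the individual's own PCR results, and no section uses a group by-day rate for them.
- *Comparisons with the control, or the duration analysis, are biased.* The listed UAM1 stools end at about Days 26-27 (Appendix 3), so daily comparisons cannot use follow-up stools. AUC stops at Day 28, the shedding index uses Days 7-28, and Kaplan-Meier keeps subjects who ceased earlier in the estimate.
- *The overstatement is ten- to twenty-fold in OPV-primed subjects.* That needs 5-10% extended, and the documents give no shedding duration for this population.

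**Conclusion.** The concern holds in a narrow form. Followed literally, SAP 6.7.1 yields by-day positivity and combined mean titre after about Day 42 that are overstated by about 1/f, with f the fraction still sampled. The first-round factor is about 2.8 or 1.7 under the two Phase 1 medians, and larger in later rounds.

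The 1/f result rests on released subjects staying negative. The numerical factors also rest on exponential durations, on medians from IPV-primed adults, and on follow-up rounds about three weeks apart. Stools that replace a missing last sample would dilute the effect somewhat.

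The affected outputs are exploratory and descriptive. Nothing in the primary or secondary analyses changes, and the rates on scheduled days stand. The correction is still worth making before the tables are produced, because the error is predictable and easily removed.

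**What to change.** In SAP 6.7.1, state that by-day summaries of PCR positivity and of combined titre are limited to the scheduled days (0-10, 14, 21, 28 and 42), and that stools collected after the last scheduled sample enter only the Kaplan-Meier analysis and the listings. A matching clause in the synopsis paragraph on viral shedding would keep the two documents aligned.

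If later days are to be tabulated, use as denominator all subjects in the group with a known end-of-schedule PCR status, and count those already released as PCR-negative as negative, with titre 0. Note in SAP 5.3 that missing completely at random is not assumed for follow-up stools.

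The cost is one or two sentences, plus a derived denominator if the alternative is chosen. No new data are needed.

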1. INTRODUCTION

1.1 BACKGROUND INFORMATION

In 2013 the Global Polio Eradication Initiative (GPEI) launched the Polio Eradication and Endgame Strategic Plan with the objective to end all polio disease globally. The 4 main objectives of the Polio Eradication and Endgame Strategic Plan are: to detect and interrupt all poliovirus transmission, to strengthen immunization systems and withdraw the historic oral polio vaccine (OPV), to contain poliovirus and certify interruption of transmission and legacy planning.

The global effort to eradicate polio has made significant progress with only 3 countries remaining with endemic wild-type poliovirus transmission—Nigeria, Afghanistan and Pakistan. In 2017, only 22 cases of paralytic poliomyelitis due to wild poliovirus (all type 1) have been reported globally, compared with 37 for 2016. Conversely, 95 cases of circulating vaccine-derived poliovirus (cVDPV) cases have been reported in 2017 – all due to the type 2 component of OPV.

For a long time, trivalent oral polio vaccine (tOPV, incorporating poliovirus types 1, 2, and 3) was the preferred vaccine for polio control and eradication. Global use of this vaccine has enabled the eradication of wild-type poliovirus type 2. Despite these advantages, most industrialized countries have transitioned to inactivated polio vaccine (IPV), primarily because OPV has the major disadvantage of causing paralytic disease in rare cases. It can cause vaccine-associated paralytic poliomyelitis (VAPP) in vaccine recipients and close contacts at an estimated rate of about 4.7 per million births (range: 2.4-9.7) globally. Moreover, in settings of poor immunization coverage, the live vaccine virus can mutate in ways that confer the transmissibility and neurovirulence properties of wild viruses, leading to polio outbreaks caused by these altered viruses known as circulating vaccine-derived polioviruses (cVDPVs). Most cVDPVs are due to the type 2 component of OPV. Several outbreaks of cVDPV2 have been documented since 2000 and most are controlled by means of focused immunization campaigns using tOPV, and more recently, also using monovalent OPV2 with or without inactivated polio vaccine (IPV). While OPV is more effective than IPV in interrupting transmission in settings of poor sanitation and hygiene, as long as the type 2 Sabin is in use, the risk for cVDPV exists and polio cannot be entirely eradicated from susceptible populations.

As part of the Polio Eradication and Endgame Strategic Plan, the Strategic Advisory Group of Experts on immunization (SAGE) called for a globally synchronized switch from tOPV to bOPV in routine immunization programs (i.e., withdrawal of OPV2) as the first step towards complete withdrawal of all oral polio vaccines. To mitigate the risks associated with this switch, SAGE recommended the addition of at least a single dose of inactivated polio vaccine (IPV) to routine immunization programs prior to withdrawal of OPV2. Adding IPV should result in a reduction of the risk of paralytic poliomyelitis if exposure to a type 2 virus occurred after OPV2 withdrawal, an improved response to any future use of a monovalent type 2 polio vaccine in the case of an outbreak, a reduction of transmission of a reintroduced type 2 virus; and boosting of immunity to the remaining wild poliovirus serotypes 1 and 3.

All countries in the world that used tOPV switched to bOPV in April 2016. Following this switch, mOPV2 is only reserved as a stockpile option for outbreak response. However,

with on-going outbreaks of type 2 cVDPV in Syria and DRC more than a year and half from the global cessation of routine OPV2 use and the small but important risk of seeding new vaccine-derived circulation with outbreak response use of mOPV2 pose a challenge to long-term and complete eradication of any type 2 circulation. The novel OPV2, with reduced risk of generating new vaccine-derived circulation offers promise in this regard and could be an important tool to sustain eradication.

